18.2 Deep Phenotyping- Data Analysis/Statistical Methods

18.2.1 Overview

This study will focus on identifying mechanistic predictors of treatment response in cLBP. We will use QST, fMRI, and measures of inflammation and ANS function to identify key neurobiological markers of cLBP that can be used *a priori* to infer what treatments are likely to work in different participant endotypes. In exploratory analyses, we will also examine changes in neurobiological markers following treatment. These analyses will help us to determine how these treatments uniquely affect pain mechanisms, a critical step for the development of new efficacious analgesics.

18.2.2 Preliminary Analysis of NPC Data

Prior to the primary analysis (primary treatment outcome will be *PROMIS Pain Interference*) descriptive statistics will be used to characterize the NPC measures, including aspects of data quality. Summary statistics for all key variables will be produced. All data will be passed to the Informatics Core, that need to be combined with self-report and behavioral measures from the BPC (assessing treatment response), for multivariate analyses and building of predictive models. The NPC will also identify high priority variables based on preliminary analyses. For instance, network-whole brain connections associated with pain subtypes (high centralized pain) that meet family-wise statistical correction or stimulated inflammatory markers/QST metrics that show robust associations with clinical characteristics, will be noted. The NPC will also help identify neurobiological markers that are supported by previous work (e.g., DMN-insula connectivity).

We will also conduct exploratory analyses to examine the mechanism of action of specific treatments. Changes in connectivity, QST, inflammatory and ANS patterns following each of the phase 1 treatments will be performed using paired sample t-tests.

We will measure the potential mediation effect of biomarkers (e.g., QST, inflammatory markers, fMRI measures) as the proportion of the treatment effect explained by the biomarker (change in the treatment regression coefficients when the biomarker is included in the model). For all models, we will use appropriate interaction terms to model effect modification. We will use bootstrap methods to estimate standard errors for the proportion of explained treatment effects, and Wald tests to evaluate the mechanistic (mediation) effect. Handling of missing data will include analysis of reasons for missingness using multinomial logistic regression. Sensitivity analyses will include missing data imputation by predictive-matching algorithms and missing data exclusion under a missing-at-random assumption.

19 Human Subjects Protections

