Group Level Analysis. Seed and network-to-whole-brain connectivity maps will be entered into a multiple regression model in SPM with change in pain interference (post minus pre-treatment) as a covariate of interest. Age and sex will be entered as covariates of no interest. Although not the primary objective of Aim 3, we will also conduct exploratory analyses to examine the mechanism of action of specific treatments. Changes in connectivity patterns following each of the phase 1 treatments will be performed using paired sample t-tests in SPM12. Resulting maps are thresholded at $p < .001$ uncorrected voxel threshold with $p \leq .05$ FDR significance corrected for multiple comparisons.

Graph Theory Analyses. Using Graph Theory Analyses the brain is defined as a network of 264 non-overlapping nodes (10 mm spheres) connected by edges or links.^{161,162} These nodes and the preprocessed fMRI data are entered into the Conn functional connectivity toolbox to create Fisher z-transformed bivariate correlation (Pearson's r) matrices (264 x 264) for each participant. To exclude weak or spurious connections, matrices are thresholded beginning with the strongest 5% connections and proceeding in steps of 5% up to 40% density, resulting in binary undirected graphs containing the most significant edges. Using the Brain Connectivity Toolbox,¹⁶³ we will calculate the following graph theoretical measures to assess global (efficiency, modularity, rich-club) and nodal (hub status) network properties, as previously published.¹⁶⁴ To assess hub status, we will calculate eigenvector centrality which takes into account the connectedness of a node, in addition to the connectedness of that node's neighbors. Hub status will be assigned to a node if the eigenvector centrality is greater than one standard deviation above the group mean.^{165,166}

Group Level Analysis. We will determine if hub status and rich club organization predicts treatment response. Individual hub measures will be entered into regression analyses to predict ($p < .05$) association with change in pain interference pre- versus post-treatment.

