Best model selection. We will select best models using the unbiased Bayesian Information Criterion (BIC) and use 10-fold cross-validation to protect against overfitting the model. To deal with potentially high-dimensional phenotype variables and other demographic and clinical covariates, regularized regressions will be considered. Penalties in the likelihood function will follow the Elastic Nets family with LASSO favored for its feature elimination potential. Alternative machine-learning model-free algorithms (random forests, SVMs) will be utilized for comparison, using the binary form of the response variables.

Characterizing the predictive performance. Cross-validated and BIC-based measures of explained variation will be used to characterize the predictive potential of the continuous response models. This analysis will be supplemented with ROC analysis based on the binary form of the response variables. We will use the cross-validated and kernel-smoothed area under the ROC curve (AUC) as an appealing measure of the predictive potential with good interpretability. Order effects will be considered during secondary analysis.

Causal analysis. We will conduct exploratory analysis of causal relationships between the light and deep phenotypic factors and the analgesic and secondary response variables. We are interested in particular causal analyses potentially implicating neurobiological and inflammatory biomarkers (deep phenotyping variables) as having a mechanistic role in the mediation of the treatment effects of light phenotypic measures. Specifically, we will measure the potential mediation effect of the deep phenotype biomarkers as the proportion of the treatment effect (PTE) explained by the biomarker. PTE is represented by a relative change in the treatment regression coefficients when the biomarker is included in the model relative to the coefficient before inclusion. We will use bootstrap methods to estimate standard errors for the proportion of explained treatment effects. Wald test statistic of the form (change in regression coefficient)/(bootstrap Standard Error) will be used to test for the presence of the mediation effect.

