The study aims to identify which interventions are most efficacious for different patient phenotypes. The primary analysis will explore how treatment response depends on patient phenotype. Secondary analyses will compare dynamic treatment regimens by patient phenotype. The SMART study does not include a control group because the efficacy of the four treatments has already been shown for the population of cLBP patients.

[figure not shown]
Study team members will not be blinded to patient treatment assignment.

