### 9.3 Objective 3 Analysis Plan

**Objective 3:** Identify the mechanisms that explain the causal treatment effects.

The primary analysis for the exploratory objective 3 (specific aim 2) will involve a series of mediation analyses in order to identify the mechanisms that underlie the differential treatment responses. This analysis will use light phenotyping data from T2 and the interim assessment conducted at the midpoint of the first-stage treatment period. Second-treatment stage data will not be used for this analysis. Investigators did not propose a light phenotyping-based mediator for the Duloxetine treatment. Thus, a mediation analysis based on light-phenotyping data will not be carried out for this study arm.

The study does not include a control group since each of the four therapies have been previously shown to be effective for treating cLBP. As a result, the mediation analyses will be conducted by treatment group. Within each treatment group, the proposed treatment modifier will play the role of the exposure in the mediation analysis. Hypothesized mediators were determined by the study investigators and are listed in Table 6 by treatment arm.

For example, consider the PT/Exercise treatment group. Investigators expect that individuals who both receive the PT/Exercise treatment and have lower self-perception of their own efficacy will respond better to the PT/Exercise intervention and have lower PROMIS Pain Interference scores at follow up. They believe that this effect is attributable in part to changes in the patients fear avoidance beliefs and avoidance behaviors. The mediation analysis will assess whether greater pain catastrophizing is associated with a greater reduction in fear avoidance beliefs, which leads to greater improvement in pain interference scores.

The outcome measure for each mediation analysis will be the PROMIS Pain Interference score measured at T3. The exposures and mediators will be measured at T2 and the first treatment-stage midpoint, respectively.

*Table 6 Hypothesized Mediation Analyses by Treatment.*

Treatment	Mediation Analysis Exposure (X)	Expected treatment mediator (M)
MBSR	PROMIS Pain Catastrophizing	Experiences Questionnaire Score
PT/Exercise	Pain Self-Efficacy Score	Fear Avoidance Beliefs Questionnaire
Acupressure	Fibromyalgia Screening Score	GSS-8

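### Paired within-arm tests of change in the deep measures cannot show treatment-specific mechanisms; add a between-arm comparison, and report the SAP 9.3 indirect effects against the other arms

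*Protocol*

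**What the plan says.** On change in the deep measures, Protocol 18.2.2 states: "Changes in connectivity, QST, inflammatory and ANS patterns following each of the phase 1 treatments will be performed using paired sample t-tests". Protocol 10.2.1 plans the same for resting-state imaging: "Changes in connectivity patterns following each of the phase 1 treatments will be performed using paired sample t-tests in SPM12", there with a p<.001 voxel threshold and FDR correction. Both are labelled exploratory. Neither document states another test of before-to-after-treatment change in a deep measure, and the SAP does not mention the paired tests. Protocol 18.2.1 gives their purpose: "These analyses will help us to determine how these treatments uniquely affect pain mechanisms".

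On the comparator, SAP 5.1 says: "The SMART study does not include a control group because the efficacy of the four treatments has already been shown". SAP 9.3 draws the consequence for mediation: "As a result, the mediation analyses will be conducted by treatment group". It adds: "Within each treatment group, the proposed treatment modifier will play the role of the exposure in the mediation analysis". The mediators in SAP 9.3 are light-phenotype questionnaires measured mid-treatment, and the outcome is T3 pain interference.

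The Protocol also has a different mediation plan, for deep biomarkers. Section 18.1.5 (causal analysis) says: "PTE is represented by a relative change in the treatment regression coefficients when the biomarker is included in the model". Section 18.2.2 repeats it as a "change in the treatment regression coefficients when the biomarker is included in the model" and adds interaction terms. The SAP does not carry this plan forward.

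**The concern.** The question is comparative (what does this treatment do that the others do not?), but the stated test of change is not. Between Deep Visit 1 (week 6) and Deep Visit 2 (week 15) several things move besides the assigned treatment: the natural course of pain in people randomised because they had not clearly improved, a second exposure to sensory testing and scanning, and continued access to PainGuide. A paired test adds all of these to the treatment effect. If they are common to the arms, some arms will cross 5% and others will not, by chance alone, and the pattern can be read as a set of distinct mechanisms.

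This bears on the part of Aim 3 that infers mechanisms of action. It does not touch the primary endpoint or the prediction analyses. The other three randomised arms are a concurrent comparator for the same measures, and the paired tests do not use them.

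**Working it through.** **Inputs from the documents.** 160 deep participants, 40 per treatment (Protocol 18.1.5, SAP 6); two-sided 5% (Protocol 18.1.5); no more than 15% missing (Protocol 18.1.5), so 0.85 × 40 = 34 per arm; 102 per arm for light measures (SAP 6).

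**Input not in the documents.** The size of any shared drift or retest effect. I take d = 0 to 0.4 SD of the change score as an assumed range.

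**1. The plan's own figure.** The nearest stated power is 81% to detect a within-arm correlation of 0.43 with n = 40. By Fisher's z, power = Φ(atanh(0.43) × √37 − 1.96) = Φ(0.4599 × 6.083 − 1.96) = Φ(0.84) = 79.9%. Adding the bias term r/(2(n−1)) gives 80.8%. The figure reproduces, but it concerns prediction within an arm. No power is given for the paired tests or for any between-arm difference in change.

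**2. Paired tests when only shared drift is present.** For one scalar measure the chance that a given arm is significant is p = P(|T| > 2.023), with T noncentral t on 39 df and noncentrality d√40. The arms contain different patients, so P(at least one of four) = 1 − (1 − p)⁴.

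| Drift d | p per arm, n=40 | At least one arm, n=40 | At least one arm, n=34 |
|---|---|---|---|
| 0 | 5.0% | 18.5% | 18.5% |
| 0.1 | 9.5% | 32.8% | 30.7% |
| 0.2 | 23.5% | 65.7% | 60.0% |
| 0.3 | 45.7% | 91.3% | 86.8% |
| 0.4 | 69.4% | 99.1% | 97.9% |

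The zero-drift row is four-test multiplicity only; what exceeds it is drift. At d = 0.3 all four arms are significant together in only 0.457⁴ = 4% of trials, so arms that drifted equally will usually look different.

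**3. Between-arm tests on the same data.** A shared drift cancels in a difference between arms. In 20,000 simulated trials of 4 × 40 at d = 0, 0.2, 0.3 and 0.5, one-way ANOVA on change rejected in 5.2%, 5.1%, 5.2% and 4.6%. A single one-arm-against-three contrast rejected in 5.1%, 5.1%, 4.9% and 4.9%.

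**4. Price in precision.** The SE in SDs of change is 1/√40 = 0.158 for the paired test, √(1/40 + 1/120) = 0.183 for one arm against three, and √(1/40 + 1/40) = 0.224 for two arms. The differences detectable with 80% power are 0.45, 0.51 and 0.63 SD.

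**5. SAP 9.3 mediation.** The indirect effect is α₁β₂. Adding a constant to every patient's M and Y changes the intercepts and leaves α₁ and β₂ alone. A simulation agrees (n = 102, 4,000 runs, both paths significant as a stand-in for the bootstrap interval). With a true X–M–Y path, the mean indirect effect was 0.089 both without and with a 1-SD shift in M and Y, flagged in 70% of runs either way. With no X–M path, it was flagged in 3.8% and 3.9%. Drift is therefore not the problem here. The problem is that the exposure is a baseline trait, not treatment. A prognostic X–M–Y path that exists under every treatment yields the same indirect effect in each arm, and a single-arm analysis credits it to that arm's treatment.

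**The case against.** The strongest reply is that the plan does compare arms. The proportion-of-treatment-effect mediation in Protocol 18.1.5 and 18.2.2 rests on treatment coefficients, which with four active arms and no control are contrasts between arms. SAP 9.1.1 and 9.1.2 also fit all arms jointly. This stands: a reader might infer that the plan makes no comparison between randomised arms, and the documents do not support that. But the first analysis asks how much of a treatment effect on outcome a biomarker accounts for, and the second concerns moderation. Neither is stated as a test of whether a deep measure changed differently by arm.

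Other points also have weight:

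- **Drift is reduced.** Participants are familiarised before sensory testing and MRI (Protocol 10.1, 10.2), and SAP 5.1 says the run-in helps control regression to the mean. The run-in ends before Deep Visit 1, so neither measure removes change between the two deep visits.
- **The decision rule is assumed.** No section says that significance in one arm will be called a unique mechanism, and SAP 7.5 favours intervals and effect sizes over p-values. The percentages show what such a reading would cost. They do not describe a declared procedure.
- **Imaging maps differ.** The single-test 5% arithmetic does not describe maps thresholded at p<.001 with FDR, although that correction does not remove a shared shift either.
- **Shared mechanisms are plausible.** The Protocol invokes descending or central inhibition for MBSR, exercise and duloxetine. A between-arm test is weak for an effect that several arms share.

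**Conclusion.** The point holds for the paired tests. They describe within-arm change, and they cannot separate treatment from anything else common to the arms or support a claim that an effect is unique to one treatment. Under the stated assumptions (one scalar measure, 40 per arm, equal drift in all arms, 5% significance read as a finding), the chance of at least one spurious arm runs from 19% with no drift to 99% at 0.4 SD. The drift sizes are mine, so the range matters more than any single figure. Because the analyses are exploratory, this is a change worth making and not a threat to the main result.

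SAP 9.3 is a separate, lesser point about specificity. Two stronger readings are tempting and should be dropped. Shared natural course or retest effects do not bias the within-arm indirect effect, because they go into the intercepts. Nor is that effect non-zero whenever X, M and Y are correlated: β₂ is conditional on X and can be zero while all three correlate.

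**What to change.** 1. **Protocol 10.2.1 and 18.2.2.** Add a between-arm comparison as the test for any treatment-specific claim: ANCOVA of the Deep Visit 2 value on randomised arm, adjusted for the Deep Visit 1 value, age and sex. Run the four-arm test first, then each arm against the other three with intervals. For maps, fit a between-arm model of the difference images. Keep the paired tests, labelled as description of within-arm change. Since a participant may be eligible for only three treatments (Protocol 8.1), state how eligibility is handled, for example by limiting each contrast to people who could have received that arm.
2. **SAP 9.3.** Fit each mediation model in the other arms as well, and report the target arm's indirect effect minus theirs, with the planned bootstrap interval, before calling a path treatment-specific. The relevant questionnaire rows in SAP Table 1 carry no arm-specific footnote; confirm that the mid-treatment values are collected in all arms.
3. **Reconcile the two mediation plans.** State whether the proportion-of-treatment-effect analysis in Protocol 18.1.5 and 18.2.2 is kept, and if so add it to the SAP.

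**Cost.** Wording and some extra analysis, with no new data. The detectable difference rises from about 0.45 to 0.51 SD of change (40 against 120) or 0.63 SD pairwise, and power for a difference in indirect effects will be low. Without an untreated arm these tests show differences between treatments, not absolute effects. A mechanism shared by several arms would be diluted, so a null between-arm result must not be taken to rule it out; the SAP should say so.

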19.1 Potential Risks

Overall, subjects taking part in the current study will be exposed to risks that are felt to be similar to those encountered in a standard clinical practice and would be deemed as having no more than a moderate risk level. The potential risks are described below and rated in terms of severity (*Table 8*) and likelihood of Occurrence (LOI) as defined in Table 5. The likelihood of occurrence is a composite measure of 1) the likelihood that a potential cause results in a hazardous situation, and 2) the likelihood that the hazardous situation results in harm. The LOI reported below is the score AFTER all identified controls have been put in place to mitigate risk.

Table 5 Likelihood of Occurrence Index (LOI)

Category	Description
Frequent	Occurrence of harm almost certain during the life of the product; History of harm resulting from failures exists from previous or similar designs
Probable	Occurrence of harm reasonably expected to occur during the life of the product
Occasional	Occurrence of harm may occur during the life of the product
Remote	Occurrence of harm unlikely to occur during the life of the product
Improbable	Occurrence of harm unexpected during the life of the product; History shows no occurrences of harm resulting from failures in previous or similar designs

Potential Risk – Breach of confidentiality. A breach of confidentiality will be considered a “definitely related” Serious Adverse Event. As such, it will be reported to the IRB within 7 days of occurrence, and a remediation plan will be put in place immediately.

Potential Risk - Blood draw. There is a slight risk of developing a small hematoma (bruise) at the site of the blood draw. There is a lot a slight risk of the patient passing out due to a vasovagal response with the blood draw.

Potential Risk – Discomfort associated with assessment questions. Some of the questionnaires can be considered personal in nature as they query about medical, symptom, and psychological well-being. Any participant becoming distressed while completing questionnaires will be encouraged to seek clarification from the local research staff at the study site or if any questions are unclear or troubling. All participants are told that they have the option to skip troubling questionnaire items and terminate participation without penalty and/or will be assisted in arranging medical/ psychiatric help including, if necessary, emergency treatment.

Potential Risk- Discomfort associated with Pro-Diary- Accelerometer - Ecological momentary assessment (EMA). Risks of completing ecological momentary assessments (EMAs) on the PRO-Diary (wrist-worn monitor) include discomfort, frustration, and the potential hassle of interruption of daily routine. These risks will be minimized by allowing participants to initiate the wake- and bed-time assessments when it is convenient for them and by allowing participants to opt-out of or postpone EMAs that are not convenient for them (they will be shown how to silence the monitor/delay reporting). These risks will also be minimized by keeping the assessments as brief as possible. Participants may also experience discomfort from wearing the PRO-Diary, especially if they are not used to wearing a watch on a daily basis. This risk is extremely rare in our experience collecting data. We will minimize this risk by offering participants choices of wrist band types and by telling them that it may take a few days to get used to wearing the PRO-Diary.

Potential Risk - Treatment Interactions – PainGuide. All participants will continue to receive care from their physician of record throughout the study. During the 6-week run-in period, all individuals will be given access to an online self-management resource, but this is a “therapist-less” intervention and therefore no additional contact is made with the participant except for initial orientation to the website. This program has been provided to patients for years with no recorded adverse events. Nonetheless, patients are always informed to contact study staff with any concerns or questions.

Potential Risk – Discomfort associated with the self-management intervention. The self-help interventions could cause emotional discomfort in as much as participants are asked to monitor their symptoms and create plans for better pain control and functionality. We expect negative effects to be extremely rare given that the behavioral self-management techniques included in PainGuide have been available to the public for over 10 years and have been embedded in efficacy trials by us and other researchers with few or no adverse effects.

Potential Risk – Treatment Interactions – Physical Therapy and Exercise. The overall risk to participants is minimal. The most likely risk is the temporary increase in muscle soreness, mild pain, or temporary fatigue from the physical therapy treatment. The physical therapy visit also involves self-report assessment of history

and symptoms to help tailor the treatment. We have summarized the risks in the Table 6 below, and provided additional detail in the accompanying text.

Table 6. Summary of Risk Profile

Procedure	Risks	LOI	Seriousness
Physical therapy -- Manual therapy, joint mobilization, directional preference exercises	Muscle soreness Back pain Fatigue Bruising	Occasional Occasional Occasional Improbable	2 2 2 1
Self-Report of Medical History & Symptoms	Psychological distress	Improbable	1-3

Physical therapy includes a manual therapy component which may cause temporary mild muscle soreness and increase in pain due to physical manipulation by the therapist. For the vast majority of people, these symptoms subside within 2 hours of treatment and many people report feeling better after the treatment is applied. The exercises may cause temporary fatigue. There are no known long-term risks associated with participant in the proposed research as many of the task-specific

Self-Report of Medical History & Symptoms: The thoughts and feelings that go along with having chronic back pain might be magnified by having to answer personal questions about one's condition. In particular, answering questions about one's health condition and function might contribute to feelings of despondency.

Potential Risk - Treatment Interactions – Mindfulness-Based Stress Reduction. While MBSR is a behavioral intervention generally regarded as safe, clinically significant adverse events have been reported from engaging in mindfulness practices (e.g., feelings of derealization, exacerbation of psychiatric symptoms or clinical deterioration). During MBSR, participants will meet weekly with the psychotherapist delivering the intervention, who will monitor for clinical worsening of depression and other psychiatric symptoms, including any self-harm or suicidal ideation or intent, and will continue to receive care from their physician of record throughout the study. In addition, participants will engage in light stretching or yoga poses that may cause temporary mild muscle soreness. Furthermore, patients are always informed to contact study staff with any concerns or questions.

Potential Risk – Treatment Interaction – Acupressure. Self-acupressure is a safe intervention. From our previous 3 clinical trials over the past 10 years using this acupressure point formula, we have observed no serious adverse events associated with the study intervention. Our most recent and largest trial of self-acupressure in fatigued cancer survivors (N=288),⁶³ had 6 adverse events related to acupressure, and all were non-serious cases of mild bruising at acupressure sites. There are no known long-term risks associated with self-acupressure. To minimize the chances of bruising, participants will be trained by the acupressure instructor in how to apply the correct amount of pressure with the AcuWand. Specific attention will be paid to not apply too much pressure. The AcuWand has a built in “buzzer” to notify the study participant when the correct amount of pressure is reached, which will minimize chances of bruising. Phone calls will also be made to the participants for the first 2 weeks of self-acupressure by the study coordinator to monitor progress and answer questions. The participant is free to withdraw from the intervention at any point if the self-acupressure intervention becomes uncomfortable.

Potential Risk – Duloxetine. Duloxetine will also be administered as it typically would be by an experienced provider, again focusing on slow gradual dose escalation. Participants will be warned about the most common

side effects with this drug include nausea, vomiting, nausea, dry mouth, constipation, diarrhea, fatigue, difficulty sleeping, dizziness, light-headedness, mood swings, sexual dysfunction, and rarely, allergic reaction. All of these side effects are thought to be less common with slow gradual dose escalation, and many (especially gastrointestinal intolerance) typically get better over time. The most serious adverse effect associated with duloxetine, and one which causes us to modify our exclusion criteria for the entire study, is the increased risk of suicidality with initiation of this drug, especially in individuals under age 25. Thus, we exclude individuals under age 25 or with a history or active suicidality from participating in our MRC study. Additionally, duloxetine is a category C medication with unknown risk to fetus. Participants will be advised of this and will be asked to either abstain from sexual activities or use an acceptable method of birth control.

Potential Risk - MRI. Prior to inclusion in the study, the presence of potential MRI risks, such as pacemakers, surgical clips or metallic surgical devices will be excluded by medical and surgical history using a standard review form. The overall risk to participants is minimal. The most likely risk for is the time burden associated with completing study procedures. fMRI, DTI and ¹H-MRS may result in some slight discomfort from the noise produced by the MRI machine and the MRI's magnet's ability to pull metal objects toward it. This pull can cause metal objects in the body (e.g. surgical clips or staples) to move and cause bleeding or disruption of surrounding tissue. Also, claustrophobia may be problematic, and individuals will be screened for this problem. Lastly, there is some proposed risk to pregnant women receiving an MRI scan.

The MRI scans themselves are painless and not uncomfortable, although it does require the subject to lie still with the head and part of the body confined in a tunnel-like device. Fast imaging sequences, such as those employed in this study, have the potential to induce peripheral nerve stimulation (PNS). PNS can be described as a light touching sensation on the skin surface and may cause mild discomfort, but is not harmful to the patient. Other than those described above, there are no known biological risks due to exposure to the magnetic fields such as those that will be utilized in this study.

Potential Risk – Pheno Device.

Risk	LOI	Severity	Mitigation
Slight low back muscle fatigue or soreness the following day similar to a light workout	Occasional	1	Participants will be instructed to move as fast and as far as they can COMFORTABLY. Researchers will be trained on all study procedures to protect participants.
Exacerbation of pain symptoms or condition following the motion assessment if the participant is a back pain patient		3	Participants will be instructed to move as fast and as far as they can comfortably. Researchers will be trained on all study procedures to protect participants. Researchers will make it clear from the beginning of the study that participants can stop participating at any time. This will help ensure that anyone experiencing any type of discomfort will not be motivated to complete the study despite their best health interest.

			
Participants will not be permitted to participate until inclusion/exclusion criteria are assessed and satisfied.
 
Patients will not be permitted to participate until they have been cleared by one of our researcher clinicians.
 
Patient participants will conduct research visits in a clinical environment under close supervision.

Irritation, pinching, rubbing, or sticking of skin from harness components	Improbable	2	
Participant touching materials use fabrics and materials that are standard in clothing.

Participant loses balance when performing motion test and falls	Improbable	3	
Participants will be instructed to move as fast and as far as they can comfortably.
 
Researchers will be trained on all study procedures to ensure participant safety.
 
Patient participants will conduct research visits in a clinical environment under close supervision.

Breach of Confidentiality	Improbable	3	
The software has undergone a risk assessment by UMHS IT and has been approved to store PHI.

Cross contamination of infectious element between patients	Improbable	3	
The device will be cleaned thoroughly using hospital-grade sanitizing wipes after each use.
 
Participants will wear the motion sensor harness over their clothing to avoid contact with skin.

Allergic reaction to harness materials	Improbable	3	
Participant-touching materials do not contain latex and use fabrics and materials that are standard in clothing

Electrical leakage from IMU sensors resulting in shock	Improbable	1	
Motion sensors are an off the shelf product that have been made for wearable human use. Motion sensors are battery powered, encased in plastic, and are low voltage devices. The harnesses are constructed of electrically insulating materials, providing an additional layer of protection. The charger system has a product safety mark.

			Device will be evaluated by UMHS Clinical Engineering to be within the prescribed tolerance for patient contact.
Participant piercings or other wearable materials (e.g. insulin pump) snag during motion testing	Remote	2	Software will include instructions and researcher user training to instruct participants to remove or secure all wearables that could snag during motion prior to testing.
Sensors interfere with performance of other devices, including medical devices	Improbable	2	Sensors are tested to Federal Communications Commission for Bluetooth Transmission standards and the IMU sensors' Bluetooth signal is similar to that of a wireless mouse or headphones. Device will be evaluated by UMHS Clinical Engineering to be within the prescribed tolerance for patient contact.

